**Assessment of Comorbidities: Psychiatric and Symptom Assessments:**

Interval assessments will be performed by Research Staff. Self-report scales will be completed by the participant. (Scales are included in the appendix)

The following will be administered:

- The Structured Clinical Interview for DSM-5 Axis I (SCID-5-RV) , and
- The Structured Interview for DSM-5 Personality (SCID-5-PD) 
- Beck Depression Inventory-II (BDI-II)
- Beck Anxiety Inventory (BAI)
- Posttraumatic Scale Checklist-5 (PCL-5),
- Modified Fear Survey (MFS),
- Barratt Impulsivity Scale (BIS-11)
- Traumatic Life Events Questionnaire (TLEQ)

The SCIDs and clinician rated symptom scales will be performed by a rater who has been trained and assessed for reliability by an expert in psychiatric diagnostic nosology. All scales administered have established reliability and validity.

**Assessments of Quality of Life and functioning:**

- Montreal Cognitive Assessment (MoCA): v8.1 at baseline and v8.2 at endpoint
- The Quality of Life in Epilepsy-31 Scale (QOLIE-31)
- Family Assessment Device (FAD)
- Longitudinal Interval Follow-Up Evaluation Range of Impaired Function (LIFE-RIFT)
- Symptoms Checklist–90 (SCL-90)
- Oxford Handicap Scale (OHS)
- Global Assessment of Function (GAF)
- Clinical Global Impressions Scale (CGI)
- Neurobehavioral Symptoms Inventory (NSI)

**Follow-up assessment:**

The PNES/ES follow-up questionnaire (ESTXFU) is used after the treatment portion of the study and will be used for secondary longitudinal analysis. There will be 2 follow up sessions (months 8 & 12 after the participant's first CBT-Sz session) the interviewer will ask participants questions regarding the seizure frequency and treatments using this questionnaire (ESTXFU). These sessions will be conducted by research staff either in person or via phone call.

**Participants with TBI without PNES or PTE will complete/have:**

- The consent process (giving written permission to take part in the study)
- MRI Safety screening
- Diagnosis validation
- Baseline and endpoint measures at the time of fMRI's (the same as Seizure participants)
- Two MRI brain scan approximately 13 weeks apart
- Follow-up at 8 and 12 months from the first fMRI with the TBI follow up survey (TBITXFU) (this assessment will ask about symptom frequency and treatments and will be conducted by research staff either in person or via phone call).

**Allowable windows:**

Research staff will aim for participants to meet the desired timeline, unexpected events occur in people's lives, therefore, for this study the researchers will allow for up to a 3 day window on either side of the desired timeline for completion of the study procedures and assessments before identifying them as a deviation. The CBT-Sz sessions may also be completed in up to 16 weeks.

**Neuroimaging assessment:**

After consent and eligibility has been completed. All participants will have a functional MRI at 2 time points, after consent within the 2 weeks before the start of the first CBT-Sz session, and at least 13 weeks after the first MRI (within 2 weeks after the last CBT-Sz session). The fMRIs take approximately 60 minutes. The functional MRIs will be conducted at either the Providence VA Medical Center Neuroimaging Suite or the Brown University MRI Research Facility (MRF).

These Functional MRI (fMRI) tasks were previously developed and tested in healthy controls and patients with epilepsy and PNES.

The fMRI emotional faces task: Participants will be presented a pseudo-randomized series of faces with different emotional expressions. Unique facial images are displayed followed by a screen with a “+” in the center. In order to monitor attention to the task, participants will be asked to respond to the gender of the face using a response button held in their right hand. Immediately after fMRI, participants are asked to indicate the expression on each of the previously presented faces. Activations with this task are robust and the task allows for evaluating several types of emotions. This task will occur at both fMRI's.

#### The fMRI stress task:

The fMRI task elicits mild-to-moderate level of stress similar to the level of stress experienced in everyday situations.

For both fMRIs, the stress tasks consists of a control math task (CMT) designed to be non-stressful and a stress math task (SMT) intended to induce a moderate amount of psychosocial stress. The SMT is based on the Trier Social Stress Task and the Montreal Imaging Stress Task. All participants perform the CMT followed by the SMT. All instructions (during practice and fMRI) are scripted to assure uniformity of the experimental conditions. CMT includes subtraction problems in which participants have to select the correct answer from two choices by pushing the corresponding button on the response box. Throughout the task, participants hear different pre-recorded messages that provide positive evaluative feedback regardless of actual performance. After completing the CMT and prior to SMT initiation, participants are told that “researchers” will be evaluating their performance and will give them feedback during the task, that for each question they have a variable time of 1-5 seconds to respond in order for their answer to count, and for their data to be used and to be reimbursed the full compensation of \$100, they needed to achieve an unspecified number of correct answers based on the average score for people of their age and level of education (i.e., deception is used to induce mild-to- moderate stress response). During the SMT, Participants perform more difficult subtraction problems than the CMT with three answers to choose from. Participants also hear different pre-recorded messages, all of which provide negative evaluative feedback regardless of actual performance (mild-to- moderate psychosocial stress). Both tasks also include instances of a tone condition where participants are instructed to press “1” or “2” on the response box while hearing a train of tones. The tone condition was designed to monitor attentiveness during the task regardless of actual performance. At the end of the imaging session each participant will be debriefed and informed that they earned the maximum amount of reimbursement irrespective of their performance.

This stress task target the emotion processing (limbic) circuits, including medial-frontal and medial- temporal regions.

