## **STUDY DESIGN OVERVIEW**

Our plan is to investigate the cerebral underpinnings of emotion and stress processing in 88 individuals with confirmed PNES and 88 individuals with confirmed PTE and 88 individuals with a history of TBI without seizures (PNES or PTE) matched for psychiatric comorbidities (TBI control subjects – CS). In addition to the between group comparisons (PNES vs. PTE vs. CS), we will examine the changes in brains' response to fMRI probes after receiving treatment (CBT-Sz), a non-pharmacologic therapeutic approach that is used for the treatment of difficult to control seizures in patients with PNES and PTE. All participants in the 3 groups will receive fMRI scans at approximately 13 week intervals. Including CS in the neuroimaging and symptom surveys portion will allow us to determine the stability of signals between and within the individuals and to control for the effects of psychological and psychiatric comorbidities.

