**Participant Compensation**

Compensation will be according to each site's acceptable local policy, i.e. gift cards or (ETF) electronic transfer of funds, etc. Compensation will be based on study visit time and effort and to help with transportation/parking costs. PNES and ES participants will receive up to a total of \$800 for study involvement. Compensation will be \$100 per fMRI (for scan and testing/tasks at the fMRI session) which will be given after the completion of the fMRI and up to \$600 at the last CBT-Sz session (\$50 for completion of each of the 12 sessions).

The TBI controls will receive up to \$200 for their time and effort. They will receive \$100 for each fMRI session (for scan and testing/tasks at the fMRI session) which will be given after the completion of the fMRI.

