**4.1 Power analysis**

Our power analysis is based on our preliminary neuroimaging and clinical data, and data regarding number needed to be evaluated in neuroimaging studies to reliably demonstrate differences between

groups in cognitive studies. Based on our preliminary data for the fMRI stress task ([name], unpublished), given the large effect size (Cohen's *d*) of 0.88, when the sample size is 14 people per group, a *t*-test of two related samples with 5% two-sided significance will have about 85% power to reject the null hypothesis that there is no difference in pre-intervention and post-intervention fMRI measures in limbic structures (medial frontal cortices and amygdala). In a recently analyzed study of the emotional faces fMRI task, 12 participants per group were sufficient to show significant differences between participants with PNES, ES and controls in emotion control brain circuits. ([name], et al, HMB, under review) It is possible that the effect size may not be as large in ES as it is expected in PNES. For this study, we expect 25 participants per group to be sufficient to account for the possibility of a more conservative effect size (e.g., 0.65). With the expected 50% responder rate to the cognitive challenge (CBT-Sz), 50 per each group (PNES, PTE, controls) will allow to test the within groups and between groups differences. Adding additional 24 participants per group will allow controlling for two most frequent comorbidities in our patients (12/condition; depression / anxiety and PTSD; 50+24=74). With anticipated attrition rate of up to 20% ( $74 \times 0.2 = 14$  to 15 per group) a sample of 88 Veterans with PNES, 88 Veterans with PTE, and 88 Veterans with TBI but no PNES/PTE can address the study hypotheses and control for the confounders including comorbidities.

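### Participants appear to be told after MRI 1 that pay did not depend on performance, yet the same deception is repeated at MRI 2, so within-group change on the stress task cannot be credited to CBT-Sz alone

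*Combined protocol and SAP*

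**What the plan says.** The section on the fMRI stress task, within 3.7 Study Evaluations, makes three statements that have to be read together.

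- The task is the same at both scans: "For both fMRIs, the stress tasks consists of a control math task (CMT"), followed by the stress math task.
- The stressor rests on a cover story. Participants hear that researchers are evaluating them, and that use of their data and the full $100 depend on reaching an unspecified score. The section says so openly: "deception is used to induce mild-to- moderate stress response".
- Once scanning is over, "each participant will be debriefed and informed that they earned the maximum amount of reimbursement irrespective of their performance".

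Participant Compensation sets $100 per fMRI, "which will be given after the completion of the fMRI", so full payment also follows MRI 1.

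Section 4.1 gives its one explicit power figure, about 85%, for a paired test on this task. The null hypothesis is "no difference in pre-intervention and post-intervention fMRI measures in limbic structures". Objective 3 looks for physiological change in the brain as evidence of response to CBT-Sz, and Hypothesis 2 attributes change in the fMRI signal to CBT-Sz.

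There is a comparator. The Study Design Overview states: "All participants in the 3 groups will receive fMRI scans at approximately 13 week intervals". The TBI controls do not receive CBT-Sz. Imaging data analyses (section 4) proposes a hierarchical linear model (HLM) for change over time but names no group-by-time contrast.

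**The concern.** A deception works as a stressor only while it is believed. A participant who learns after MRI 1 that pay was never tied to the score meets the same threat at MRI 2 with one of its elements already disclosed. The two scans then differ in the strength of the stimulus as well as in whether therapy has taken place.

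In a single-group pre/post comparison these two differences are completely confounded, so a change produced by disclosure could be reported as neuroplasticity from CBT-Sz. A weaker stressor at MRI 2 also leaves less response in which to see a real effect, in every group.

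**Working it through.** **Inputs from the plan (4.1 Power analysis).** Effect size 0.88 with 14 per group; paired t-test, 5% two-sided; 88 enrolled per group; attrition up to 20%. Completers: 88 × 0.80 = 70.4, taken as 70.

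**Input not in the plan.** The size of any disclosure shift. It is assumed here, in SDs of the change score, and shown as a range.

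**Step 1: reproduce the plan's figure.** Paired t-test power comes from the noncentral t with df = n − 1 and noncentrality d√n. For n = 14 and d = 0.88 the noncentrality is 0.88 × √14 = 3.29, and power is 86.0% against the stated figure of about 85%. A test of two independent groups of 14 would give 61.1%. The powered contrast is therefore the within-group pre/post change.

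**Step 2: within-group test, no CBT-Sz effect, disclosure only.** Same formula with n = 70, noncentrality = shift × √70 = shift × 8.37.

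| Assumed shift (SD) | Noncentrality | Probability of p < 0.05 |
|---|---|---|
| 0.20 | 1.67 | 38% |
| 0.30 | 2.51 | 70% |
| 0.35 | 2.93 | 82% |

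The result does not hinge on n = 70. A shift of 0.3 SD gives 55% at n = 50 and 72% at n = 74, the other two group sizes that appear in section 4.1.

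**Step 3: change in a seizure group minus change in TBI controls.** Two-sample t, 70 per group, df = 138, noncentrality = difference ÷ √(1/70 + 1/70) = difference × 5.92, with the same SD of change in both groups.

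- Equal shift in both groups: the difference is 0 and the error rate stays at 5%.
- Shift differing by 0.2 SD: noncentrality 1.18, false rejection 22%.
- Shift differing by 0.3 SD: noncentrality 1.77, false rejection 42%.
- True CBT-Sz effect of 0.65 SD of change (the plan's conservative effect size, applied here to the difference in change) with an equal shift: noncentrality 3.85, power 97%. With 50 per group it is 90%.

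So the control-adjusted contrast is affordable at the planned size and removes any common shift. It does not remove a differential one.

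**Step 4: interval between disclosure and reuse.** The schedule puts MRI 2 at least 13 weeks after MRI 1. Sessions may run to 16 weeks (Allowable windows), with MRI 1 up to 2 weeks before the first session and MRI 2 up to 2 weeks after the last: 16 + 2 + 2 = 20 weeks.

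**The case against.** **The timing and content of the debriefing are not certain.** The text speaks of the imaging session in the singular, and the appendix holding the task scripts is not in the supplied text. Only the disclosure about pay is spelled out. A reader might infer that participants learn the negative feedback was scripted and so know the whole threat is empty; the section does not say that. The harder problems, the time limits and the negative messages all remain at MRI 2. This stands, and it limits the claim to one element of the stressor. Payment after each scan still favours a debriefing at each, and nothing supplied defers it.

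**The design already has a control.** TBI participants have the same two scans without CBT-Sz and are included partly to show signal stability; section 4.1 mentions between-group as well as within-group differences. A shift common to all groups would show in the controls and cancel. A uniform shift would also not create the correlation with symptom improvement that Aim 2 looks for. Both points stand. What they leave open is that no group-by-time test is specified, that the groups are defined by diagnosis rather than randomised, and that nothing ensures an equal shift.

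**The direction is unknown.** Two stronger readings are tempting. One is that PNES has the largest baseline response and so loses most from disclosure. Hypothesis 1 says only that PNES is the most abnormal, which could mean a smaller response. The other is that disclosure acts in the same direction as treatment. Hypothesis 2 gives no direction for the fMRI change, and the power calculation is two-sided. Neither reading is supported: a differential shift could mimic a CBT-Sz effect or hide one.

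**Conclusion.** The point holds for within-group change on the stress task. As written, the protocol repeats a deception after disclosing one of its named elements, and the contrast with the stated power cannot tell the consequence from CBT-Sz. With no treatment effect and 70 completers, assumed shifts of 0.2 to 0.35 SD would be declared significant in 38% to 82% of studies. Comparison with TBI controls restores the 5% error rate if the shift is equal across groups; if it differs by 0.2 to 0.3 SD, false rejection is 22% to 42%, in either direction.

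This rests on reading the debriefing as taking place at each session, and on assumed shifts, since the documents give no estimate. If the task appendix already defers the debriefing, the main text should say so.

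It would go too far to infer that the trial's imaging results are compromised as a whole. The group comparison at MRI 1 precedes any debriefing, and the emotional faces task as described uses no deception. Neither is affected.

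**What to change.** 1. Amend the stress-task section so that the deception is disclosed once, after MRI 2 or at withdrawal. Pay the $100 after MRI 1 without explaining how it was determined. Both changes are subject to IRB agreement.
2. Name change in each seizure group minus change in TBI controls (the group-by-time term in the HLM) as the test for the stress-task claim about CBT-Sz. State that within-group change alone will not be attributed to CBT-Sz.

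**Cost.** A protocol and IRB amendment, a revised debriefing script and a short addition to the analysis section; no extra visits, staff or scans. Debriefing is delayed by 13 weeks or more, about 20 if sessions run to 16 weeks. With attrition of up to 20% expected, participants lost before MRI 2 must be debriefed through another contact. The IRB will need to weigh both.

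The first change is not complete on its own. Full payment after negative feedback is itself a hint, and the task is familiar the second time. Anyone already debriefed at MRI 1 cannot be made unaware again. The second change is therefore needed alongside the first.

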#### MRI tasks scanning protocol

##### **See appendix - MRI tasks and scanning protocol.**

These tasks and instructions are currently in use at the UAB Imaging Center in studies that involve patients will be implemented at each study's imaging center.

##### **Retention strategies**

The retention/attrition-minimization strategies for this study will include weekly reminder contacts and utilizing tele-medicine visits when travel is restricted, which will be used as needed. Participants with

ongoing seizures cannot drive; therefore we will aim to a) assure that they have appropriate transportation or b) will conduct sessions via telephone.

**Adherence and Competency (A&C):** Treatment adherence and competency of intervention measures will be closely monitored by session review and digital-audio/video. To ensure that the therapists are conducting sessions in a highly competent fashion, rating scales designed to assess therapist competence and adherence will be utilized. Measures of therapist competence will be used to: a) verify therapist competence prior to treating study patients and b) to monitor sessions for quality assurance. The therapist competence in the sessions will be rated using the Clinical Management Scale of the Collaborative Study Psychotherapy Rating Scale (CSPRS) developed by the Collaborative Psychotherapy of Depression. For CBT adherence, a modified Cognitive Therapy Scale (CTS) that was designed and validated for CBT.

In addition to the above scales, each session will be rated as "acceptable" or "unacceptable." Ratings will be done by study staff reviewers at RIH. Potential problems or deviations will be noted by the reviewer for discussion with the therapist.

### **Risks/Benefits Assessment**

#### **Potential Risks to Participation**

Assessment risks: Completing self-reports, questionnaires and the emotional processing MRI task could result in feelings of anxiety, depression, or psychological distress.

MRI risks: MRI imaging is generally considered to be safe but accidents, injuries, and even deaths have occurred during MRI procedures in the past. These events are extremely rare if all safety precautions are followed. Serious injuries can also occur if participants wear metal objects, like jewelry, eyeglasses, metallic cards, or clothing or eyeshadow with metal; these must be removed before the MRI process. If participants have metal pacemakers, metallic dust in the eyes (from metal eye injuries or history of metal work), or other metal implants that make them ineligible for MRI procedures, they will not participate in the study due to safety reasons. All childbearing age female participants will be required to be using birth control until completing the second MRI and to undergo a pregnancy test prior to each MRI, and those who test positive prior to their first MRI will not be allowed to participate in the study due to safety reasons. Research staff and the MRI technician will ensure that all proper screening is completed before deciding MRI eligibility and safety. All safety procedures will be carefully monitored according to standard MRI procedures and local MRI policy.

Treatment risks: A risk of participating in this study is that the treatment may not be as helpful as hoped. It is unlikely, but some parts of the treatment may lead to increased symptoms and possible need for hospitalization. Discussing distressing situations during the sessions may also temporarily increase symptoms.

Loss of privacy: Another possible risk is loss of privacy. Every effort will be taken to protect the confidentiality of participation in this study.

#### **Safety Monitoring Plan**

The Principal Investigator will have primary responsibility for day-to-day monitoring of participant safety, and the quality of operations in all data collection, data cleaning and transfer activities.

All adverse events (AEs) occurring during the course of the study will be collected, documented, and reported to the PI. The study investigators will follow all AEs to the point of a satisfactory resolution. A study participant may be withdrawn from the study if the medically responsible investigator determines it is the best decision in order to protect the safety of a participant. All AEs will be assessed to determine if they meet criteria for a Serious Adverse Event (SAE). SAEs will be reported to each IRB according to their policy. In the event that a participant either withdraws from the study or the investigator decides to discontinue their participation due to a SAE, the participant will have appropriate follow-up medical monitoring. Monitoring will continue until the problem has resolved or stabilized with no further change expected, or it is deemed to be clearly unrelated to participation in the study.

If during the study participants are found to develop suicidal intent, medical or other mental health problems they will be triaged for appropriate care, according to good clinical practice and the safety protocol.

This multi-site study includes a Data Monitoring Committee (DMC). See Addendum F for the DMC plan.

**Risk management and emergency response:**

The study's safety and seizure protocol is attached in the Appendix.

**Potential benefits**

Individuals who receive CBT-Sz may receive the benefit of reduction of seizures and or increased quality of life. There is no other direct benefit to participants. Participants may contribute to the scientific understanding of the effects of CBT-Sz on the brain which may lead to more understanding about the brain in individuals with seizures and for researchers to learn the best non-drug treatment for seizures which may help other individuals with seizures.

